MOBILE Intervention in College Students with Elevated Blood Pressure

Version Date: 05/19/2021

Protocol and Procedures

Protocol and Procedures

Aim 1 Formative research design. We will recruit two student panels (4-5 students each) to further refine the **MOBILE** intervention and assist in developing measures used in the study. We will recruit one set of student panel at a time. This 4-month phase will enable the team to design an extensive list of SMS messages tailored to different levels of motivation. In a 4-week intervention, enough messages are needed to ensure no message will be sent more than twice. Given 3 levels of motivation (1-low, 2-moderate, and 3-high), each level requiring different prompting messages, at least 42 (28 days x 3 levels = 84/2 = 42) messages need to be created across the 3 levels. The team will draft an initial set of messages, drawing content from the American Heart Association high BP recommendations;⁶⁰ each message's behavioral suggestions will correspond to each of the 3 motivation levels. Students will be surveyed to rank the effectiveness of each message; they will be asked to assess how clear, compelling, engaging, and motivating each message is in itself and how effective each message might be in propelling them to action. The investigative team will identify strong and weak messages, characterizing what makes strong messages strong. The team will then build a revised list of messages, discarding the weakest, or use what we have learned to strengthen the weaker messages. We will repeat this process with the second group of students using the revised list of messages and use those results to build a stronger final set of messages to be used in the implementation phase of the study. This iterative approach will also refine the study's motivational scale and self-report survey. This phase will be held via zoom with no in-person contact.

Aim 2 and Exploratory Aim Research Design. The proposed pilot study will use a randomized two-arm intervention and control group design to test the preliminary impact of the **MOBILE** intervention. The PI will be involved in all aspects of study and will train a research assistant (RA) to provide the educational session, monitor subjects, and address technology challenges.

Aim 2 Sample size. We will recruit 32 subjects to be randomized to an intervention and control arm with a ratio of 1:1 ($n = 16$ per study group), using a random number generator. A sample size comparable to a prior study of cellular phone and internet-based intervention on BP reduction that showed medium to high effect sizes (ES $f = 0.395$) on BP reduction.⁴⁹ Using an estimated ES of $f = 0.39$ for the within-subject effect (Time), we conducted a power analysis for a mixed design ANCOVA with 2 groups, 2 measurements per subject, and $r = .5$ for the bivariate correlation between two measures tested at $\alpha = 0.05$. To achieve 70% power for the significance test of the within-between interaction effect, a sample of $N = 28$ will be needed. Anticipating a 7-11% attrition rate⁴⁹ based on the previous study,⁴⁹ an initial $N = 32$ will be needed to achieve 70% power to test preliminary impact. The low power is a limitation; we will attempt to recruit more within the timeframe to reach a higher power level.

Aims 1 and 2 Site for subject enrollment. UNLV is the largest university in Nevada with over 30,000 undergraduate and graduate students, and it is most diverse university in the nation. This increases the potential for inclusive recruitment of different race/ethnicities that reflect the changing demographics of the state and nation.

Aim 2 Enrollment and recruitment. We will use recruitment strategies that have been successful in the PI's previous studies, including posting research flyers around campus, UNLV Rebel Announcements, UNLV Today (monthly), Student E-Newsletters from Department (SEND), and UNLV Graduate & Professional Student Association. Recruitment will occur face-to-face with students at sites around campus (once campus is opened). Subjects will be screened privately for inclusion (1. During the initial zoom meeting going over the informed consent in addition to 2. Having high blood pressure, meet via face-to-face following CDC guidelines for 5-10 minutes).

Aim 2 and Exploratory Aim Study Procedures - MOBILE Intervention

Baseline data collection. Baseline data collection (using Qualitrics) will occur before the start of the educational session, described below. Subjects with blood pressure value less than 120/80 mm Hg during this visit (second blood pressure reading) will no longer qualify for this study. The gold standard BP measurement using a sphygmomanometer through auscultation will be taken twice, five minutes apart to be averaged. Other baseline data include: anthropometry (height and weight), Automated Self-Administered 24-Hour Dietary Assessment Tool (ASA24) focusing on sodium intake, pre-test Hypertension Knowledge-Level Scale (HK-LS), and initial motivational level assess (using Qualitrics) using the study's iPads. We have two research iPads that are only designated for this project. The subjects will not use their own devices and the link are not send to subjects. It is already set up to collect data from the subjects. We locked the screen on the iPads so only the questionnaires can be accessed.

Aim 2 Educational session, all subjects. The PI or RA will provide a brief one-on-one or group educational talk (no more than 2 subjects, to separate intervention and control group subjects) before the 4-week trial on the importance of SMBP, elevated BP regarding CVD risk, the role of motivation in adopting lifestyle behavior, and specific behaviors to reduce BP. This is akin to HTN risk reduction advice received in an office visit.

Aim 2 MOBILE Intervention Group. Following the educational session, intervention subjects will receive a Withings BP cuff and Health Mate app will be installed on their smartphone. *The research team will create a username (subject's ID for the study to maintain confidentiality) for each subject.* By consenting, subjects will grant us access to their recordings and direct access to app manufacturer data on them. As a second layer, we will also ask the subjects to send the research team their daily blood pressure value to ensure we have the data and continual daily communication. We will show them how to use the Health Mate app, upload Withings BP cuff readings, upload historical data to the cloud, read trend lines in their record, rank their daily motivational level, and answer a brief SMS question about whether they completed the behavioral change task encouraged by the daily message. A one-page instruction sheet with the research team's contact information will be provided. In addition to addressing questions, the session will offer the opportunity to practice using and entering data on the app. Subjects' use of the app will be assessed and followed-up within 72 hours by the RA to ensure subjects' comfort level using the instruments and app. Subjects will be instructed to take their BP daily, before their first meal and encouraged to avoid prior alcohol and caffeine intake as well as physical activity. They will be instructed to rate their motivational level as low, moderate, or high via SMS when transmitting their BP value. Their level will trigger the appropriate behavioral change SMS prompt. Thus, a subject at a high motivational level – because they feel good about having their BP in the normal range – will receive an encouraging text message ("keep up the good work") along with a prompt to complete a difficult task (e.g. do some form of physical activity for 30 minutes). On a low motivation day, a subject might be encouraged to look up low-salt salad dressing recipes online. Subjects will receive a reminder SMS if they have not provided their daily BP. *This is not a physical activity or dietary intervention; therefore, specifically physical activity or dietary education will not be provided, rather this is a behavioral intervention that encourages the subjects to engage in healthy behaviors that they have previous experience to draw from, with additional information provided during the educational session, to reduce their blood pressure value.*

If we haven't heard from the subject for more than 7 days, we will invite the subject to a meeting to explore why the subject hasn't been participating. Such meetings will give us an opportunity to identify barriers and challenges subjects are experiencing and to remind them why they enrolled in the first place. An RA will contact each subject two times during the 4-week intervention to (a)

explore the acceptability of and engagement with the intervention and (b) reinforce study participation. Subjects can always withdraw from the study if they wish to do so.

Aim 2 Control Group. Following the educational session, the control group subjects' BP, ASA24 (sodium intake), and pre-test knowledge on HTN will be obtained (using Qualtrics). Four weeks later, the subject will be scheduled for a follow-up meeting to collect each subject's BP, ASA24, and post-test knowledge on HTN (using Qualtrics).

Aim 2 Post-intervention data collection and intervention engagement. We will schedule a post-intervention meeting with each subject for data collection (gold standard BP) and return of the Withings BP cuff (intervention group only). We operationalize acceptability, the key Aim 2 outcome, as the subject's favorable perception of the **MOBILE** intervention as being appropriate and reasonable in addressing their elevated BP, convenient to use, easy to apply to their daily lives, and effective in addressing their elevated BP both currently and long-term. Data on acceptability and other study variables will be gathered using questionnaires and open-ended questions in a semi-structured exit interview (using Qualtrics). The research team will monitor the intervention for subject acceptability operationalized as active and continual participation in the intervention (receiving the subject's daily BP value), and favorable responses to the tailored change behavior SMS. The team will also measure engagement with the intervention, operationalized as the extent to which the subject followed the self-monitoring protocol. The self-report survey and semi-structured interview script will be created and implemented by the research team during the formative phase. The intervention subjects will be informed that they may delete the Health Mate app at any time once their participation is completed. The research team will no longer have access to their BP data once they completed the study.

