MOBILE Intervention in College Students with Elevated Blood Pressure

Version Date: 05/19/2021

Statistical Analysis Plan

Statistical Design and Power

Sample size. We will recruit 32 subjects to be randomized to an intervention and control arm with a ratio of 1:1 ($n = 16$ per study group), using a random number generator. A sample size comparable to a prior study of cellular phone and internet-based intervention on BP reduction that showed medium to high effect sizes (ES $f = 0.395$) on BP reduction.⁴⁹ Using an estimated ES of $f = 0.39$ for the within-subject effect (Time), we conducted a power analysis for a mixed design ANCOVA with 2 groups, 2 measurements per subject, and $r = .5$ for the bivariate correlation between two measures tested at $\alpha = 0.05$. To achieve 70% power for the significance test of the within-between interaction effect, a sample of $N = 28$ will be needed. Anticipating a 7-11% attrition rate⁴⁹ based on the previous study,⁴⁹ an initial $N = 32$ will be needed to achieve 70% power to test preliminary impact. We acknowledge that the low power level is a limitation in our pilot study; therefore, we will attempt to recruit more within the timeframe to reach a higher power level.

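### The Protocol contradicts itself on whether controls' baseline is taken before or after the arm-separated educational session, and with randomisation timing unstated, post-allocation exclusions differing by arm are not ruled out

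*Protocol*

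**What the plan says.** Protocol, Baseline data collection, places baseline measurement ahead of the educational session and makes no distinction between arms. The measures are auscultatory BP, height and weight, the ASA24 sodium recall, the hypertension knowledge pre-test and the motivation rating. The same paragraph holds the disqualification rule: "Subjects with blood pressure value less than 120/80 mm Hg during this visit (second blood pressure reading) will no longer qualify for this study".

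Protocol, Aim 2 Educational session, describes a talk given to all subjects, one-on-one or in groups of "no more than 2 subjects, to separate intervention and control group subjects". The arm must therefore be known by the time of the talk.

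Protocol, Aim 2 Control Group, gives a different order: "Following the educational session, the control group" has BP, ASA24 and the knowledge pre-test obtained. The only other control measurement described there is four weeks later, so this one is the controls' baseline. Protocol, Aim 2 MOBILE Intervention Group, gives no baseline after the session; for that arm only the general baseline paragraph applies.

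On numbers, Protocol, Aim 2 Sample size, says "We will recruit 32 subjects to be randomized to an intervention and control arm with a ratio of 1:1", "using a random number generator", and gives no time point. The SAP repeats this, requires 28 evaluable subjects for 70% power, and inflates to 32 on one ground: "Anticipating a 7-11% attrition rate". Neither document says how a subject who fails the BP check after randomisation would be counted or replaced.

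**The concern.** Two problems follow, and the first does not depend on when randomisation takes place.

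**Baseline timing.** The Exploratory Aim compares the arms on change in BP, sodium intake and hypertension knowledge. The talk covers elevated BP and cardiovascular risk, self-monitoring and behaviours that lower BP. A control baseline taken after it is not the same quantity as an intervention baseline taken before it. Knowledge is the clearest case. A pre-test after teaching already contains what was taught, so controls' measured gain shrinks while the intervention arm's gain includes the effect of the talk. The difference in gain would then favour MOBILE even if the messages added nothing. Reported sodium intake and BP can also be affected, although the documents give no basis for a direction or size.

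**Exclusions.** BP is both an outcome and the qualifying measure. If controls' reading follows an arm-separated session, a disqualifying value could remove a control after allocation, while an intervention subject would be removed, if at all, before the session. No text keeps the allocation from the person taking the manual reading. With 16 per arm, one or two exclusions on one side could shift baseline balance. They would also use up numbers reserved for attrition.

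**Working it through.** **1. The order of events, side by side**

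| Step | Baseline data collection (all subjects) | Aim 2 Control Group |
|---|---|---|
| BP, ASA24, knowledge pre-test | before the session | after the session |
| <120/80 disqualification | at this visit, before the session | not mentioned |
| Arm known | by the session | by the session |
| Randomisation | not stated | not stated |

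The two columns cannot both hold for a control subject. For an intervention subject only the first applies.

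**2. The plan's own sample size**

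Inputs (Protocol and SAP, Sample size): 28 evaluable; attrition 7% to 11%.
Formula: N = evaluable / (1 − attrition), rounded up.
- 7%: 28/0.93 = 30.1, so 31.
- 11%: 28/0.89 = 31.5, so 32.

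The planned 32 reproduces, and it is an allowance for attrition alone.

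**3. Room left for any other loss**

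Room = 32 − 28/(1 − attrition).
- 11%: 32 − 31.5 = 0.5 subject, so none.
- 7%: 32 − 30.1 = 1.9 subjects, so one.

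**4. Number to randomise if BP failures fall after randomisation**

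The documents give no failure rate, so x is an assumption. N = 28 / ((1 − x)(1 − attrition)), rounded up.

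| x | at 7% | at 11% |
|---|---|---|
| 5% | 32 | 34 |
| 10% | 34 | 35 |
| 20% | 38 | 40 |
| 30% | 44 | 45 |

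If the check comes before randomisation, 32 is unaffected.

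**5. Illustration of power when only controls are lost**

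Assumptions: 16 per arm randomised, 11% attrition in both arms, 15% or 30% of controls excluded, and the plan's 70% taken as true at 14 + 14. For an F test with 1 and 26 degrees of freedom at α = 0.05, 70% power corresponds to a noncentrality of 6.66. Noncentrality scales with n1·n2/(n1 + n2), which is 7 at 14 + 14.
- Intervention completers: 16 × 0.89 = 14.2.
- 15%: controls 16 × 0.85 × 0.89 = 12.1; total 26.3. Factor 6.54; noncentrality 6.66 × 6.54/7 = 6.22; power about 67%.
- 30%: controls 16 × 0.70 × 0.89 = 10.0; total 24.2. Factor 5.86; noncentrality 6.66 × 5.86/7 = 5.58; power about 62%.

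The 70% anchor could not itself be reproduced. With f = 0.39 and r = 0.5, the usual within-between interaction formula (noncentrality f²·N·m/(1 − r), with m = 2 measurements) gives 98% power at N = 28. That is a separate issue. Here it means only that the 67% and 62% are conditional on the plan's own claim.

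**The case against.** The best defence is that the baseline paragraph governs. It covers all subjects, comes before the first step that uses the arm, and words the BP rule as eligibility. There is also an earlier face-to-face screen for high BP (Protocol, Aim 2 Enrollment and recruitment). On that reading, subjects are checked, then randomised, then taught; the 32 are those who qualified, and the sample size stands. The control-group sentence would be loose drafting, and it does not repeat the 120/80 rule.

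Much of this stands. A reader might infer that the plan sorts subjects by arm before the BP check, and does so explicitly for controls. The documents do not support that. No time of randomisation is given, the baseline paragraph alone is compatible with checking before allocating, and the control-group order rests on one section that another contradicts. A reader might also remove 15% to 30% from both arms, which on the same calibration gives about 63% to 54% power. The text offers a route to post-allocation loss for controls only, so that range should not be used.

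It is also fair to say that the between-arm comparison is exploratory, that acceptability is the key Aim 2 outcome, and that both documents admit low power and hope to recruit more. That hope has no number attached and is aimed at higher power, not at replacing failures.

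What the defence does not remove is the contradiction itself. Staff who follow the control-group section as written would take one arm's baseline after the talk.

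**Conclusion.** The concern holds as an internal contradiction with a practical consequence. One section puts controls' baseline before the talk and another puts it after. Following the second would give the arms non-comparable baselines for all three outcomes of the Exploratory Aim. This part needs no assumption about randomisation.

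The exclusion part is weaker: post-allocation exclusions that differ by arm are not ruled out, but they are not prescribed either. If they occurred, the planned 32 would absorb none at 11% attrition and about one at 7%. Any power loss is conditional on an assumed failure rate. The 67% to 62% is an illustration for 15% to 30% of controls lost, 11% attrition and the plan's 70% accepted as stated; it is not a forecast. How a subject with only one component below 120/80 is classified would also change the rate.

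This should be corrected, because the fix is cheap and works only if made before subjects are enrolled. As the comparison is exploratory in a pilot, it does not threaten the key Aim 2 outcome, acceptability.

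**What to change.** Reconcile the Baseline data collection and Aim 2 Control Group sections so that both arms follow one order:

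1. The BP qualification check and all baseline measures, including ASA24 and the knowledge pre-test, come before the educational session.
2. Only subjects who have passed the check are randomised. Allocation may come before or after the common talk; either works. If it comes after, sessions need not be separated by arm.
3. The 32 subjects (16 per arm) are counted from randomisation, so that the 7% to 11% allowance is kept for attrition.

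State the time of randomisation in both documents, and say how any subject found not to qualify after randomisation would be counted.

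The cost is revised wording and a fixed visit sequence, with no added visit, staff or measurement. The downside is that more screen-positive students are rechecked and not randomised. At an assumed failure rate of 15%, 32/0.85 = 37.6, so about 38 must be rechecked; at 30%, 32/0.70 = 45.7, so about 46.

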Data Analysis. Aim 2: We will perform preliminary descriptive analyses on all variables, use Pearson's correlation (r) to assess relationships between primary and secondary outcome variables at each data collection point, and calculate Pearson's r to assess the stability of each outcome variable pre- and post-intervention. To evaluate feasibility and acceptability, we will use content analytic methods to identify students' likes and dislikes and suggestions for future app improvement.⁶⁵ Thematic analysis of interviews will be conducted to describe the elements of feasibility and acceptability as perceived by subjects. Participation rate will be calculated as the percentage of students enrolled out of all eligible students who are invited to participate in the study; engagement will be calculated as a percentage of students' available data out of all the intended data points. **Exploratory Aim.** "The intervention group will have a significantly greater reduction in BP and sodium intake and greater increase in HTN knowledge from baseline to completion, compared to control group." A 2x2x2 mixed design ANCOVA will be performed for each of the above primary and secondary outcomes, with Study Group (Intervention vs. Control) as the between-subject factors, years of age as the covariate. A Time effect on an outcome variable would indicate the impact of the **MOBILE** intervention on the outcome measure in college students with elevated BP.

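### Separating subjects by arm for the common educational talk means allocation is known before it, so equal delivery cannot be assured; the conflicting baseline timing must also be reconciled

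*Protocol*

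**What the plan says.** The Protocol section on the educational session is headed as applying to all subjects. On who gives it and in what format: "The PI or RA will provide a brief one-on-one or group educational talk". The group format is limited by arm: "group educational talk (no more than 2 subjects, to separate intervention and control group subjects) before the 4-week trial". There is one topic list, covering self-measured BP, cardiovascular risk, "the role of motivation in adopting lifestyle behavior, and specific behaviors to reduce BP". The benchmark is ordinary advice: "This is akin to HTN risk reduction advice received in an office visit".

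On staffing, the Aim 2 and Exploratory Aim research design says: "The PI will be involved in all aspects of study and will train a research assistant (RA) to provide the educational session, monitor subjects". No masking of the presenter, script or fidelity check is described for the talk. The plan names a random number generator but does not say when the assignment is generated or opened.

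Arm-specific material comes later. Under the MOBILE Intervention Group heading: "Following the educational session, intervention subjects will receive a Withings BP cuff and Health Mate app will be installed on their smartphone".

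On baseline timing, the Baseline data collection section says that it "will occur before the start of the educational session, described below", and its list includes BP, the sodium recall and the knowledge pre-test. The Control Group section places the control subjects' BP, sodium recall and knowledge pre-test after the session.

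The SAP's Exploratory Aim expects greater falls in BP and sodium intake in the intervention group and a "greater increase in HTN knowledge from baseline to completion, compared to control group".

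**The concern.** The talk is the only education that the control arm is described as receiving, and it is also the foundation on which the MOBILE prompts build. Its topics bear directly on the three outcomes compared between arms. A presenter who knows that a subject is about to receive a cuff and daily prompts may dwell longer on self-measurement and motivation. A subject who knows the arm may listen differently. Either would make the talk unequal although its written content is equal.

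What is at stake is the interpretation of the between-arm difference in change. If the pre-test comes before the talk, the change from baseline contains whatever the talk taught. An arm difference in delivery then sits inside the contrast, and no analysis can remove it. If baseline falls before the talk in one arm and after it in the other, the contrast is distorted even when delivery is identical.

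**Working it through.** **Step 1: is allocation known before the talk?** Talks are arranged so that subjects from different arms do not share one. Two subjects can be paired or kept apart by arm only if their arms are known. So allocation precedes the talk. The PI or RA gives the talk, the PI takes part in all aspects of the study, and nothing conceals the arm from either of them. Presenter knowledge is therefore a reasonable inference, though it is not stated.

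**Step 2: does the talk itself require separation?** The topic list contains nothing specific to one arm. The cuff, the app and the SMS training all follow the session. Separation is needed from device set-up onward, not for the content of the talk.

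**Step 3: what reaches the comparison?** The documents give no figure for this, so there is none to reproduce. Let T be the knowledge gained from the talk in the control arm, T(1 + k) the gain in the MOBILE arm, and M the effect of MOBILE after the talk. Assume that the gain persists to week 4. The between-arm difference in change from baseline is then:

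- Baseline before the talk in both arms: M + T(1 + k) − T = M + kT.
- Baseline before the talk in the MOBILE arm and after it in the control arm: M + T(1 + k) − 0 = M + T(1 + k).
- Baseline after the talk in both arms: M, as far as the talk's immediate effect goes.

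For illustration only, assume T = 1 SD and k = 0.10 to 0.30. In the first case the spurious part is 0.10 × 1 = 0.1 SD to 0.30 × 1 = 0.3 SD. In the second case it is 1 SD even with perfectly equal delivery (k = 0), and 1.1 to 1.3 SD with k = 0.10 to 0.30. The second case concerns chiefly knowledge. A 24-hour dietary recall taken straight after a talk covers intake from before it, so timing could alter what is reported but not what was eaten.

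**Step 4: effect on a test.** Inputs: r = .5 and α = 0.05 (SAP, Sample size); 28/2 = 14 per arm after attrition or 32/2 = 16 as recruited; no true MOBILE effect; a two-sided t test on change scores. The change-score SD is √(2(1 − 0.5)) = 1 outcome SD, so the noncentrality for a spurious difference d is d√(n/2).

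| d (SD, assumed) | n = 14: noncentrality, rejection rate | n = 16: noncentrality, rejection rate |
|---|---|---|
| 0 | 0, 5.0% | 0, 5.0% |
| 0.1 | 0.265, 5.7% | 0.283, 5.9% |
| 0.2 | 0.529, 8.0% | 0.566, 8.5% |
| 0.3 | 0.794, 11.9% | 0.849, 13.0% |

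These rates follow from assumed values of d. They show scale and are not evidence that such a difference exists.

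**The case against.** The strongest reply is that separate delivery is not different content. There is one topic list, one benchmark and no stated difference in length or presenter by arm, and the PI trains the RA to give the session, which is some standardisation. This stands. A reader might infer that the talk has ceased to be a common starting point, or that presenters will favour MOBILE subjects. The documents support neither inference; they show only that equality is not protected.

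Separation also has a plausible purpose: two subjects from different arms who meet at a talk could exchange MOBILE content over four weeks on one campus. This stands too, and the fix has to preserve that protection. One-on-one talks do so without anyone needing to know the arm. It is true that the plan already allows them, so grouping by arm is not universal, but nothing says that the arm is withheld from the presenter in that format.

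A reader might also infer that the talk is the main source of knowledge gain in both arms. That is not established. MOBILE subjects receive daily messages drawn from published high-BP recommendations, and these may teach as well.

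Finally, the affected comparisons are exploratory in a 32-subject pilot whose key Aim 2 outcome is acceptability. Subjects cannot realistically be masked to a cuff and SMS prompts for four weeks, so masking one brief talk removes only part of the performance bias. This limits the weight of the point, but it is no reason to keep an avoidable part of that bias.

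**Conclusion.** The point holds as a cheap improvement to the design. Allocation must be known before a talk that is meant to be the same for everyone, and no masking, script or fidelity check protects equal delivery. Any difference would be inseparable from MOBILE in the exploratory comparisons of HTN knowledge, sodium and BP. Bias is possible and not demonstrated. Its size cannot be derived from the documents, and the 0.1-0.3 SD rests wholly on the assumed 1 SD talk effect and 10-30% differential.

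The conflict over baseline timing is on firmer ground, because it lies in the text itself. Read literally for each arm, it would put the whole immediate talk effect on knowledge into the contrast. A reader might infer that the trial will in fact be run that way. The documents do not settle this, since the general baseline section is not limited to one arm. The two sections must be reconciled so that timing is identical in both arms.

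**What to change.** For every subject, use one order: baseline measures and the eligibility check; the educational talk; opening of the random assignment; then cuff and app set-up for MOBILE subjects only. In the educational session section, replace the clause about separating the arms with a statement that neither presenter nor subject knows the allocation during the talk. The assignment must be held so that the presenter cannot see it earlier. Give the talk one-on-one rather than to pairs who may end up in different arms. Amend the Control Group section so that its baseline timing agrees with the general baseline section.

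If this order proves impractical, the fallback is a fixed script or recording for both arms with a simple fidelity check, plus a stated time of allocation. That reduces unequal delivery but does not by itself settle the baseline timing, which would still need correcting.

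The cost is somewhat more presenter time, because pairs are given up, and generating or opening the assignment at the visit. If baseline, talk and set-up are not planned for a single visit, which the documents do not make clear, some rescheduling may be needed. No additional measurements are required.

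### The protocol puts the control arm's baseline both before and after the educational session; the later timing would bias the hypertension-knowledge comparison toward MOBILE

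*Protocol*

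**What the plan says.** Protocol, Baseline data collection, gives one order for everyone: "Baseline data collection (using Qualitrics) will occur before the start of the educational session, described below". The measures it lists include blood pressure, the ASA24 and the "pre-test Hypertension Knowledge-Level Scale (HK-LS), and initial motivational level assess". No arm is exempted.

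Protocol, Aim 2 Educational session, gives the talk to all subjects. Its content includes "elevated BP regarding CVD risk, the role of motivation in adopting lifestyle behavior, and specific behaviors to reduce BP".

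The two arm-specific sections then start from the same point in time but differ in what follows:

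- In Aim 2 MOBILE Intervention Group, the next step is equipment: "Following the educational session, intervention subjects will receive a Withings BP cuff and Health Mate app will be installed on their smartphone". Training on the device and app comes next. No pre-test is listed.
- In Aim 2 Control Group, the next step is measurement: "Following the educational session, the control group subjects' BP, ASA24 (sodium intake), and pre-test knowledge on HTN will be obtained (using Qualtrics". The follow-up measurement, with the knowledge post-test, is then set four weeks later.

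The SAP (Data Analysis, Exploratory Aim) hypothesises, for the intervention arm, a "greater increase in HTN knowledge from baseline to completion, compared to control group". The analysis is a mixed-design ANCOVA with age as the only named covariate. The SAP does not say when the pre-test is taken.

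**The concern.** For controls, the protocol gives two incompatible times for the same three measurements. Both places call the knowledge measure the pre-test. The control section also counts four weeks from its measurement to the post-test, so it describes the control baseline and not an extra assessment.

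The conflict differs by arm. Staff who follow each section as written would test intervention subjects before the talk and controls after it. The talk covers what a hypertension-knowledge scale plausibly asks about. A control's baseline would then already include whatever the talk taught, which lowers that arm's measured increase, while the intervention arm keeps its increase in full. Randomisation does not protect against this, because the difference arises in measurement after allocation. Adjusting for age does not restore the missing pre-education score.

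At stake is the between-arm comparison of knowledge. Blood pressure and sodium intake share the timing conflict, but no bias of known direction can be shown for them.

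**Working it through.** The plan gives no figure on this point to reproduce. The check is algebra followed by a false-positive calculation.

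**Inputs**

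- Evaluable subjects: 28, so 14 per arm; enrolled 32, so 16 per arm (SAP, Sample size). These serve only as planned sizes. The power calculation behind 28 is a separate matter and nothing here depends on it.
- Pre-post correlation r = .5 and alpha 0.05 (same section). The test is taken as two-sided, which the SAP does not state.
- E, the immediate gain in HK-LS score from the talk, in SD units: not in the documents, so a range from zero is used.
- k, the share of E still present at 4 weeks: any value.
- True MOBILE effect: zero.

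**Bias under split timing**

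- Intervention (pre-test before the talk): change = kE − 0 = kE
- Control (pre-test after the talk): change = kE − E
- Difference = kE − (kE − E) = E, for every k

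Example with E = 0.5 and k = 0.5: the changes are +0.25 and −0.25 SD, a difference of 0.50 SD in favour of MOBILE.

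**False-positive rate**

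With two time points, the Group × Time test is a comparison of mean change between arms.

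- SD of change = √(2(1 − r)) = √(2 × 0.5) = 1 SD
- SE = 1 × √(2/14) = 0.378 SD
- Noncentrality = E / SE; for E = 0.5 this is 0.5 / 0.378 = 1.32
- Rejection rate from the noncentral t with 26 df

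| E (SD) | Rejection with no MOBILE effect |
|---|---|
| 0 | 5.0% |
| 0.1 | 5.7% |
| 0.2 | 8.0% |
| 0.3 | 11.9% |
| 0.5 | 24.7% |
| 0.8 | 53.1% |
| 1.0 | 72.1% |

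Sensitivity at E = 0.5: 19% if r = .3, about 38% if r = .7, and 28% if all 16 per arm are retained (r = .5). Losing one df for age leaves the rate at about 24.6%. At r = .5 with 14 per arm, 24.6 of the 24.7 points are rejections in favour of MOBILE.

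Simulation at E = 0.5 agrees: the mean between-arm difference is 0.50 SD and rejection is 24.6% to 24.7% at k = 0, 0.5 and 1. When both arms share the same timing, whether before or after the talk, simulated rejection is 5.0% to 5.2%.

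**Pooled Time effect**

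The SAP also says "A Time effect on an outcome variable would indicate the impact" of the intervention. With both arms measured before the talk, the pooled change is kE. With split timing it is the average of kE and kE − E, which is kE − E/2. Late control testing therefore lowers the pooled Time effect by E/2, so the bias toward MOBILE applies to the between-arm test only.

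**The case against.** The strongest reply is that the control section is only loosely worded. The Baseline data collection section is the one devoted to baseline, and it sets one order for all. It also uses that visit's blood pressure as an eligibility check: subjects below 120/80 mm Hg no longer qualify. A control's blood pressure therefore has to be taken early for the check to work. This stands as evidence for the harmless reading, but it concerns blood pressure and does not settle when the HK-LS is given.

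Second, the intervention section is about devices and text messages and lists no outcome measurements at all, so its silence is weak evidence of a deliberate difference between arms. That is fair as to intent. It does not change the result, because the only baseline time given for intervention subjects is before the session.

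Third, E is unknown. The talk is described as brief, its overlap with the HK-LS items cannot be judged, and r = .5 comes from a power calculation built on a blood pressure effect. This stands. The rates are illustrations, and the excess is small up to about E = 0.2 SD.

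Fourth, this is one exploratory outcome in a 32-subject pilot. That also stands and limits the consequences. None of these points reconciles the two instructions.

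**Conclusion.** The concern holds. The protocol contradicts itself on when control-arm blood pressure, ASA24 and knowledge pre-test are taken, and neither document resolves it.

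The bias is conditional. It arises if the control section is followed while the intervention arm keeps the general baseline timing, and if the talk raises HK-LS scores at once. The between-arm knowledge difference is then overstated by E whatever is retained, and the false-positive rate rises from 5% by an amount that depends on an E the documents do not give. If every subject is measured before the session, there is no bias and the control section is a wording error. Acceptability is unaffected.

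Correction is needed before enrolment even if the error is only one of wording: once a control has heard the talk, the pre-education score is lost and no analysis can restore it.

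**What to change.** Reconcile the two sections by rewriting the first sentence of Protocol, Aim 2 Control Group, for example:

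*Before the educational session, at the same visit and in the same order as in the intervention group, control subjects' BP, ASA24 and pre-test HK-LS will be obtained.*

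Any timing common to both arms removes the between-arm bias. Pre-session timing is the natural choice because the Baseline data collection section already states it.

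Cost: one sentence in the protocol. No extra visits, measures or staff.
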